11 CRITERIA FOR REMOVAL FROM PROTOCOL THERAPY AND OFF STUDY CRITERIA

11.1 Criteria for Removal from Protocol Therapy

Subjects will be discontinued from the study treatment with the investigational drug for any of the following reasons:

- Evidence of disease progression based on RECIST 1.1 Criteria (see Section 10) in dose escalation phase.
- Noncompliance.
- Subject voluntarily withdrew his/her consent.
- Subject develops a DLT.

- Extraordinary medical circumstances: Subject who, in the opinion of the Investigator, should be discontinued for their well-being or if at any time the treatments prescribed by this protocol are detrimental to the subject's health, the subject may be withdrawn from the study (see Section 5). In this event, reasons for withdrawal should be clearly documented.
- If subject becomes pregnant or requires breast-feeding during the Treatment period.
- Subjects who are off protocol therapy instead of disease progression will need to complete End of Study Visit.
- All surviving subjects will be followed up for survival status by phone contact or subjects' clinic visit every 12 weeks for up to 24 weeks.

11.2 Off Study Criteria

- Death.
- Lost to follow-up: After Investigators or study staff have attempted to reach the subject at least 2 times over a 4-week period and failed, the subject may then be considered lost to follow-up.
- Withdrawal of consent: Subject decides to voluntarily withdraw from the study **AND** refuses collection of follow-up information.

12 STATISTICAL CONSIDERATIONS

12.1 Hypotheses

No formal statistical hypotheses will be tested.

12.2 Target Sample Size

A maximum number of 18 subjects can be enrolled in the dose escalation phase; and a maximum number of 14 subjects can be enrolled in the cohort expansion phase. A maximum of total 32 subjects can be enrolled in this Phase I study. The sample sizes for the study are not driven by statistical considerations. The study is considered as pilot and exploratory in nature to evaluate the potential dose-response relationship to facilitate dose selection for subsequent studies.

12.3 Safety and Toxicity

Toxicity graded by the US NCI Common Toxicity Criteria Version 4.0 in conjunction with MedDRA (Medical Dictionary for Regulatory Affairs) will be employed to evaluate the safety profile of the study treatments. Safety variables to be evaluated are listed in Section 9.4.

12.4 Statistical Methods

12.4.1 Analytical Sets

• The Safety Population is the group of subjects who received at least one dose of investigational product and had at least one post-dose safety assessment.

- The Immune Response Population is the group of subjects who received at least one dose of investigational product and had anti-Globo H IgG or IgM production.
- The Tumor Response Population will include all enrolled subjects.
- 12.4.2 Premature Termination and Missing Values

All available data will be displayed and utilized in data analysis. Subjects prematurely terminating the study treatment will be summarized. Listings of subjects with premature termination will be provided with the dates and reasons for termination. Missing data will not be replaced by any estimated or imputed values.

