1.2 Secondary Objective

- To assess humoral immune responses (anti-Globo H IgG and IgM production) following subcutaneous administration of OBI-833/OBI-821
- Tumor response (per RECIST 1.1 criteria)

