- For Dose Escalation Phase only: Obtain tumor biopsy/tissue samples of primary site (and distant metastases if possible) which will be tested for Globo H, SSEA-3, SSEA-4 and PD-L1 expression by immunohistochemistry (specified in Section 5.8 "Other Study Procedures"). Although fresh specimens are preferred, most subjects should have historical tumor tissue specimens available, which can be submitted to the central lab for testing. If tumor tissue samples are not available, fresh tumor tissue samples should be acquired prior to administration of investigational drug. However, in cases where tumor biopsies may not be possible, subjects are not required to submit tissue samples.
- Collect blood samples for exploratory analysis of the following biomarkers prior to administration of investigational drug:
 - Monitoring of immune response of anti-Globo H, anti-SSEA-3 and anti-SSEA-4 antibody production.
 - CTC (only in selected Taiwan sites)

- ADCC and CDC
- Administer investigational drug subcutaneously.
- Record use of concomitant medications.
- Monitor and record adverse events assessed by NCI CTCAE v4.0 post administration of investigational drug.
- Collect blood sample for the subjects with known EGFR mutations to be analyzed in the Cobas EGFR Mutation Tests in cohort expansion phase

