5.8 Other Study Procedures

Tumor tissue samples (and histology/pathology report, if possible) will be collected at Week 1 prior to administration of the investigational drug and be submitted to a central laboratory to test the expression levels of Globo H, SSEA-3, SSEA-4, and PD-L1 by immunohistochemistry, as well as other tumor markers that may be expressed in the lung, gastric, colorectal or breast tumors. Note that, subject tumor biopsy/tissue samples will be collected to test the expression levels of Globo H, SSEA-4, and/or PD-L1 will be conducted at Week 1 for data analysis purpose and not for eligibility criteria in Dose Escalation Phase. Tumor biopsy/tissue samples are mandatory for Cohort Expansion subjects to test Globo H and other tumor markers such as SSEA-3, SSEA-4, and/or PD-L1 are for data analysis purposes. Globo H expression levels will be collected and tested at screening visit for eligibility.

Blood samples will be collected at various visits shown in Table 1 and 2 and stored with the intention of performing scientific research or immunological analysis on humoral and cellular mediated immune responses, and immunogenicity of the vaccine, using in-house glycan chip and Quantitative ELISA to detect immune response and monitor tumor response by biomarkers.

These tests will include measurement of anti-Globo H IgG and IgM production. Blood samples will also be collected for exploratory analysis of various biomarkers as follows:

- Monitoring of immune response of anti-Globo H, anti-SSEA-3 and anti-SSEA-4 antibody production.
- CTC (only in selected Taiwan sites)
- ADCC and CDC
- T cell and B cell immune response (in selected Taiwan sites)
- B/T cell immunogenomic analysis (in selected Taiwan sites)
- Ex vivo immunogenicity analysis (in selected Taiwan sites)
- Cobas EGFR Mutation Tests (in selected Taiwan sites)

Tissue and blood samples will be analyzed using qualified assays by contracted laboratories under the supervision of OBI Pharma, Inc.

In order to evaluate the treatment response and the therapeutic mechanism of immunotherapies to specific tumor biology, blood and tumor samples need to be stored for present and relevant future studies in order to further explore the anti-tumor immune mechanism against specific tumor biology.

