9.2 Secondary Endpoints

- Immune response as assessed by anti-Globo H IgG and IgM production.
- Tumor response per RECIST 1.1 criteria.

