12.6 Immune Response Analysis

The results of anti-Globo H IgG and IgM titer determined by ELISA at each assessment time point per dose cohort will be summarized using descriptive statistics. Change from baseline (Week 1) will also be summarized. The maximal response, time to maximal response and the area under the response curve for each IgG type may be determined to aid the evaluation of potential dose-response relationship.

The immune response may also be analyzed and summarized based on the solid tumor cancer type as appropriate, or based on the IHC results of Globo H, SSEA-3, SSEA-4 and PD-L1 antigen at baseline (Week 1 or screening).

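### The Immune Response Population is defined by antibody production, the secondary endpoint itself; read as written, it drops sampled subjects who made no antibody

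*Protocol*

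**What the plan says.** Protocol Section 12.4.1 defines three analysis sets.

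- **Safety Population:** subjects who "received at least one dose of investigational product and had at least one post-dose safety assessment".
- **Immune Response Population:** subjects who "received at least one dose of investigational product and had anti-Globo H IgG or IgM production".
- **Tumor Response Population:** everyone enrolled.

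Section 9.2 gives the secondary immune endpoint as "Immune response as assessed by anti-Globo H IgG and IgM production", and Section 1.2 states the objective in the same terms.

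Section 12.6 says that the anti-Globo H IgG and IgM "titer determined by ELISA at each assessment time point per dose cohort will be summarized using descriptive statistics". It adds change from Week 1 and, as optional aids to judging dose-response, the maximum, the time to maximum and the area under the curve. It names no analysis set. Section 12.4.2 states: "All available data will be displayed and utilized in data analysis".

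**The concern.** The condition for entering the set is the outcome that the set is meant to describe. A subject who was dosed, gave post-dose samples and had neither IgG nor IgM is removed because the vaccine did not work in that subject. The other two sets have no such feature: one asks for an assessment whatever it shows, and the other takes all enrolled subjects.

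Two things would follow. The level of response would be overstated in any cohort that has subjects with neither isotype. The comparison between dose cohorts would be distorted if the share of subjects with production differs by dose. Section 12.2 says the study is meant to explore dose-response in support of dose selection for later studies, so these summaries are the part of the trial exposed to the problem.

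**Working it through.** **1. What the wording fixes.** Section 12.4.1 gives no cut-off and no time window for production. The only antibody threshold in the protocol, 20 µg/ml in Sections 5.4, 5.5 and 12.7, decides when cellular tests are run and not who belongs to a set. Section 12.4.2 leans towards using every result but does not redefine the set. Two readings remain, with different denominators:

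- *literal:* dosed, and antibody was produced;
- *lenient:* dosed, and an antibody result exists.

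**2. Numbers available.** The enrolment maxima are consistent: 3 cohorts × 6 = 18 in escalation, and 18 + 14 = 32 overall. Escalation cohorts start with three subjects and go to six under the rules in Section 4.1. There is no rate of production, effect size or power statement to reproduce, so everything below is an assumed range.

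**3. Effect on the mean.** Suppose k of n sampled subjects are excluded and their change is zero. The mean change in the set is then the mean in all sampled subjects multiplied by n/(n − k).

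| Sampled n | Excluded k | Factor |
|---|---|---|
| any | 0 | 1.00 |
| 3 | 1 | 3/2 = 1.50 |
| 6 | 1 | 6/5 = 1.20 |
| 6 | 2 | 6/4 = 1.50 |
| 14 | 1 | 14/13 = 1.08 |
| 14 | 4 | 14/10 = 1.40 |

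The rows for 14 are the single-dose expansion phase, where only the level is affected.

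On a geometric scale, assume a 4-fold rise in producers, none in the others, and a share p with production. The rise in all sampled subjects is 4^p: 2.0, 2.6 and 3.5 for p = 0.5, 0.7 and 0.9. The literal set shows 4 in each case.

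**4. Chance that it occurs.** The probability of at least one exclusion is 1 − p^n. For p = 0.5, 0.7 and 0.9 it is 0.98, 0.88 and 0.47 with six subjects. With 14 it is above 0.99, 0.99 and 0.77.

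**5. Effect on the dose comparison.** Let p be the share with production and m the mean change among producers, with L and H for the lower and higher dose.

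- True ratio = (pH × mH)/(pL × mL).
- Ratio in the set = mH/mL.
- Ratio in the set ÷ true ratio = pL/pH.

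| pL | pH | mL | mH | True ratio | Shown by the set |
|---|---|---|---|---|---|
| 4/6 | 6/6 | m | m | 1.50 | 1.00 |
| 6/6 | 4/6 | 10 | 20 | 13.33/10 = 1.33 | 2.00 |
| 6/6 | 4/6 | 10 | 12 | 8/10 = 0.80 | 1.20 |

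With the smallest difference in six, 5/6 against 6/6, the factor is 0.83 if the share rises with dose and 1.2 if it falls.

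**The case against.** The best answer is that production is simply this protocol's name for the measurement. Section 5.8 says "These tests will include measurement of anti-Globo H IgG and IgM production", and the procedures in Section 5 list "Monitoring of immune response of anti-Globo H, anti-SSEA-3 and anti-SSEA-4 antibody production". On that view the definition means only that a result exists, and Section 12.4.2 supports it. Section 4.1 also says that the committee which chose the expansion dose looked at data from all escalation subjects. This makes the lenient reading quite possibly the intended one. It does not remove the literal one: Section 5.8 treats production as the thing being measured, and Section 12.4.1 mentions neither a measurement nor a result.

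A second objection concerns size. Section 2.6 reports a delayed response, not an absent one, and so points only to a subject who leaves early, before antibody appears. Section 12.6 summarises by time point and Section 12.4.2 rules out imputation, so such a subject affects only the first post-dose visits (Weeks 3 and 4), an early-termination sample, and the optional per-subject maximum and area. That limit is correct for early leavers. It does not cover a subject who stays and never responds. Section 2.1 makes such a subject conceivable, since it says that the response to cancer antigens is suppressed in cancer patients.

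Third, the dose examples use invented means and six subjects in each cohort, and nothing in the protocol suggests that the share with production falls with dose. This stands: they show the direction and possible scale of the distortion and predict nothing for this trial.

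Last, a cut-off for production and the naming of sets can be left to a statistical analysis plan. That is true of missing detail. Here the protocol states a rule, and the rule as stated selects on the outcome.

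**Conclusion.** The concern holds. As written, the Immune Response Population selects on the secondary endpoint, and no other section corrects the definition. Under the literal reading, and with zero change in excluded subjects, mean change is inflated by n/(n − k): nothing if nobody is excluded, 1.2 to 1.5 for one exclusion in an escalation cohort of six or three. The high-to-low dose ratio is multiplied by pL/pH, which flattens it when production becomes more common with dose and steepens or reverses it in the opposite case. These sizes rest on assumed shares and on arithmetic means.

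The consequence is limited. The endpoint is secondary and descriptive, no hypothesis is tested (Section 12.1), and the expansion dose has been selected (Section 4.1). What is affected is the immune response summary and its use in choosing doses for later studies. It should be fixed.

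**What to change.** In Section 12.4.1, define the Immune Response Population as all subjects with at least one dose and at least one post-dose anti-Globo H IgG or IgM result, whatever its value. Require a Week 1 value only for the change-from-baseline summaries. In Section 12.6, name this set and report, per cohort, how many dosed subjects have no post-dose result. If a proportion with production is reported, treat it as an outcome within the set.

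The cost is one sentence in each section, with no new data or visits. Reported immune response figures may be lower. Subjects who leave before the Week 3 sample and have no early-termination sample would still be left out, but because data are missing and not because of their result. If the lenient reading was intended all along, the change only records it.

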12.4.3 Baseline

The baselines for clinical findings, laboratory evaluations, vital signs, physical examination, ECG, and performance status, as detailed in Table 1 and 2– Treatment and Post Treatment Periods, will be evaluated at entry.

12.4.4 Interim Analysis

No interim analysis will be performed.

12.5 Safety Analysis

12.5.1 Adverse Events

Adverse events will be regarded as Treatment Emergent (TEAE) if they started on or after the date and time of administration of the first dose of study drug, or if they were present prior to the administration of the first dose of study drug and increased in severity during the study.

Adverse Events (AEs) will be coded using the standard Medical Dictionary for Regulatory Activities (MedDRA) dictionary and grouped by system organ class and preferred term and events. TEAEs will be summarized by frequency and proportion of total subjects, by system organ class and preferred terms. Separate summaries will be given for: all events, events by CTC grade, and events by relationship to study drug. All AEs will be provided in data listings.

Subjects who died during the study will be summarized and listed. Subjects with Serious Adverse Events (SAEs) will be summarized and listed. AEs leading to discontinuation or leading to modification of drug dose will be summarized.

12.5.2 Clinical Laboratory Parameters

Each laboratory analyses will be summarized using descriptive statistics mean (standard deviation), median (range, min, max). Change from baseline will also be summarized. The incidence of markedly abnormal lab values will be provided.

12.5.3 Other Safety Parameters

Other safety parameters such as vital signs, ECGs, concomitant medications and study drug exposure will be summarized via summary tables and descriptive statistics.

12.6 Immune Response Analysis

The results of anti-Globo H IgG and IgM titer determined by ELISA at each assessment time point per dose cohort will be summarized using descriptive statistics. Change from baseline (Week 1) will also be summarized. The maximal response, time to maximal response and the area under the response curve for each IgG type may be determined to aid the evaluation of potential dose-response relationship.

The immune response may also be analyzed and summarized based on the solid tumor cancer type as appropriate, or based on the IHC results of Globo H, SSEA-3, SSEA-4 and PD-L1 antigen at baseline (Week 1 or screening).

12.7 Exploratory Analysis of Other Biomarkers

The results of exploratory analysis of other biomarkers (Anti-SSEA-3, anti-SSEA-4 antibodies, CTC, ADCC, CDC) at each assessment time point per dose cohort will be summarized using descriptive statistics. Change from baseline (Week 1) will also be summarized. Cellular immune responses (B cells and T cells) will be analyzed for 4 continuous visits after either serum anti-Globo H, anti-SSEA-3, or anti-SSEA-4 IgG reaches 20 μ g/ml after Week 8. B/T cell immunogenomic analysis will be conducted at Screening, Weeks 6, 12, 20, 64, and every 8 weeks until 8 weeks after 1st disease progression. Ex vivo immunogenicity Analysis will be conducted at screening visit. Anti-Globo H, anti-SSEA-3 and anti-SSEA-4 antibody will be evaluated by Quantitative ELISA and glycan array. Cobas EGFR Mutation Tests will be conducted at Weeks 1, 12, 40 and post treatment period 1 for all subjects with known EGFR mutations in selected Taiwan sites.

13 ADVERSE EVENTS AND SERIOUS ADVERSE EVENTS

Timely, accurate, and complete reporting and analysis of safety information from clinical trials are crucial for the protection of subjects, Investigators, and the Sponsor, and is mandated by regulatory agencies worldwide. The sponsor has established standard operating procedures (SOPs) in conformity with regulatory requirements worldwide to ensure appropriate reporting of safety information; all clinical trials sponsored by OBI Pharma, Inc. or its affiliates will be conducted in accordance with those procedures.

The investigator and/or delegated site staff is responsible for detecting, documenting and reporting events that meet the definition of an Adverse Event (AE) or Serious Adverse Event (SAE). During the study when there is a cohort safety evaluation, the investigator or site staff will be responsible for detecting, documenting and reporting all AEs and SAEs. AEs and SAEs will be collected from the start of dosing of OBI-833/OBI-821 and until the End of Study.

13.1 Adverse Events

Based on ICH guidelines, an adverse event (AE) is defined as any untoward medical occurrence in a clinical study subject administered a medicinal product. An AE does not necessarily have a causal relationship with the treatment. An AE can therefore be any unfavorable and unintended sign (including an abnormal finding), symptom, or disease temporally associated with the use of a medicinal product, whether or not related to the investigational drug. This includes any occurrence that is new in onset or aggravated in severity or frequency from the baseline condition, or abnormal results of diagnostic procedures, including laboratory test abnormalities.

Treatment-Related AEs

A treatment-related AE is an event that is considered associated with the use of a study treatment (OBI-833/OBI-821) if the attribution is possibly, probably, or definitely related by the definitions listed in Section 13.3.

Adverse events (AEs) and toxicities will be assessed throughout the study and graded according to US NCI Common Toxicity Criteria, Version 4.0, developed by the Cancer Therapy Evaluation Program at the National Cancer Institute. The criteria for unacceptable toxicities should include any \geq Grade 4 toxicity, with the exception of local skin reactions, fever, chilling, sweats, urticaria, and/or pruritis since these are common side effects of antibody/adjuvant administration, are reversible, and controlled by supportive management. Theoretically, immune complex disease as manifested by skin, joint, renal, or other manifestations could occur, but these should be rare in the absence of prior exposure to mouse protein. These will be an indication to stop therapy in the affected subjects, but accrual of new subjects may continue.

In general, Grade 1 (Mild) and Grade 2 (Moderate) adverse events are considered acceptable. Grade 3 AEs are Severe but reversible or medically manageable conditions involving major organ and organ function. Grade 4 AEs are Life-threatening consequences; urgent intervention indicated.

Any adverse event must be recorded in the subject medical records and on the eCRFs. The onset and end dates, severity, duration, effect on investigational drug administration (e.g., discontinuation), relationship to investigational drug, and administration of any other drug(s) for treatment of AEs will be recorded for each adverse event.

Subjects will be questioned and/or examined by the Investigator or his/her designee for evidence of adverse events. The questioning of subjects with regard to the possible occurrence of adverse events will be generalized as, "How have you been feeling since your last visit?" The presence or absence of specific adverse events should not be solicited from subjects.

13.2 Anticipated Adverse Events

Previous reports and clinical studies on Globo H did not present with any drug-related serious adverse effects. Adverse effects were generally mild to moderate with the most common adverse effects been mild flu-like symptoms and transient local skin reactions at the subcutaneous injection site. However, possibilities of an allergic or autoimmune reaction may occur, as with all immunotherapy and vaccines. When serious toxicities due to immunotherapy treatment do occur, please follow the guidelines for treatment discontinuation in Section 6.

13.3 Assessment of Relationship to Treatment

The Investigator must assess the relationship of any adverse event to the use of investigational drug, based on available information, using the following guidelines:

• Not related:

With no temporal relationship with administration of the investigational drug. May have negative dechallenge and rechallenge information. Typically explained by extraneous factors (e.g., concomitant disease, environmental factors, or other medications or chemicals).

• Unlikely related:

With a temporal relationship to administration of the investigational drug that makes a causal relationship improbable, and in which other medications, chemicals, or underlying disease provide plausible explanations.

• Possibly related:

With a reasonable time sequence to administration of the investigational drug, but which could also be explained by concurrent disease or other medications or chemicals. Information on treatment withdrawal may be lacking or unclear.

• Probably related:

With a reasonable time sequence to administration of the investigational drug, unlikely to be attributed to concurrent disease or other medications or chemicals, and which follows a clinically reasonable response on withdrawal (dechallenge).

• Definitely related:

Occurs in a plausible time relationship to administration of the investigational drug, and which concurrent disease or other medications or chemicals cannot explain. The response to withdrawal of the treatment should be clinically plausible.

